6.5 EVALUATIONS AT THE END OF TREATMENT

The end-of-treatment (EOT) visit will be scheduled within 31 days (\pm 10 days) after administration of the last dose of lorbinecetin, unless the patient starts a subsequent antitumor therapy, in which case the end-of-treatment visit should be performed immediately before the start of the new therapy (ideally the day before or the same day).

Patients who meet the continuation criteria and obtain a clear clinical benefit with lorbinecetin after the completion of the first two study cycles, may continue treatment outside this study under a Compassionate Use Agreement after the completion of the optional third study cycle. Should the patient continue under a Compassionate Use Agreement, the treating center must request authorization to the relevant Health Authorities and notify the Sponsor in due time. Patients, regardless of the reason for ending the treatment, will have to undergo at the end of treatment the following assessments:

- Complete physical examination (BSA and height not needed).
- ECOG PS.
- Laboratory tests (hematology and biochemistry A and B, and Calculated CLcr). Calculated CLcr [Cockcroft and Gault's formula] should be provided only if serum creatinine levels are above ULN.
- Coagulation (INR) will be repeated only if clinically indicated.
- ECG (in triplicate) and LVEF assessment.
- Adverse Events.
- Intercurrent events, concomitant disease and therapies.
- Pregnancy test in WOCBP.

Adverse events must be reported for 31 days after the last study treatment administration. All serious adverse events (SAEs) occurring within 31 days of the last study treatment administration or until the start of a new antitumor therapy, until the continuation of treatment outside this study under a Compassionate Use Agreement or death, whichever occurs first, will be reported. Beyond this period of time, only those suspected to be treatment-related SAEs will be reported (Section [8.5.2](#)). The Sponsor will evaluate all safety information that is spontaneously reported by an Investigator beyond the time frame specified in the protocol.

6.6 FOLLOW-UP AFTER END-OF-TREATMENT VISIT

After EOT, patients with treatment-related toxicities > grade 2 will be followed every four weeks until recovery to at least grade 1 or stabilization of all treatment-emergent AEs, or until the start of a new antitumor therapy, until the continuation of treatment outside this study under a Compassionate Use Agreement or death, whichever occurs first.

7. TREATMENT

7.1 DESCRIPTION OF TREATMENT

All patients will receive two consecutive cycles of lorbrena, one cycle with and one cycle without bosentan co-administration (in different order depending on the study sequence of treatment), followed by a third cycle with lorbrena alone (this last cycle optional for patients with clinical benefit).

7.1.1 Drug Formulation and Supply

Bosentan

Commercially available bosentan film-coated tablets (with strengths of 125 mg) will be provided by the Sponsor.

Lorbrena

Lorbrena 4 mg drug product (DP) is presented as a lyophilized powder for concentrate for solution for infusion in 30 mL vials and will be supplied by the Sponsor for the purposes of this study.

Before use, the 4 mg DP should be reconstituted with 8 mL of water for injection to give a solution containing 0.5 mg/mL of lorbrena. For administration to patients

as an i.v. infusion, reconstituted vials should be diluted with either glucose 50 mg/mL (5%) or sodium chloride 9 mg/mL (0.9%) solution for infusion.

The full composition of the lurbinectedin 4 mg DP and the reconstituted solution per mL is shown below:

Table 6. Composition of lurbinectedin Drug Product reconstituted solution.

Component	Concentration/vial	Concentration/vial after reconstitution
Lurbinectedin	4.0 mg	0.5 mg/mL
Sucrose	800 mg	100 mg/mL
Lactic acid	22.08 mg	2.76 mg/mL
Sodium hydroxide	5.12 mg	0.64 mg/mL

For detailed instructions on the reconstitution and dilution, refer to the latest lurbinectedin IB and the “Preparation Guide for Infusion” document.

7.1.2 Storage Conditions

Bosentan

Bosentan film-coated tablets should be stored following the instructions described in the SmPC.

Lurbinectedin

Until more information is available from ongoing stability studies, lurbinectedin DP 4 mg should be stored at $+5^{\circ}\pm 3^{\circ}\text{C}$.

7.2 ADMINISTRATION OF THE STUDY MEDICATION

Bosentan

Bosentan will be administered orally twice daily as 125 mg film-coated tablets.

In the co-administration cycles, bosentan will be administered orally twice daily in the morning and in the evening from Day -5 to Day -1 (i.e., five days before lurbinectedin infusion), and once daily on Day 1 (i.e., the day of lurbinectedin infusion), following recommendations at the Summary of Product Characteristics (SmPC). On Day 1 (i.e., day of lurbinectedin infusion), bosentan will be given immediately prior to the start of the lurbinectedin infusion. In fact, bosentan should be administered after obtaining the bosentan PK sample #1 and before the start of lurbinectedin infusion (-15 min to -1 min). In case of lurbinectedin delay (≤ 2 days), bosentan could be administered twice daily during a maximum of seven consecutive days before lurbinectedin infusion, and supplied at the study center once daily on Day 1 (before lurbinectedin infusion).

In Sequence 1 (TR), bosentan for self-administration and the patient’s diary should be given to the patient on Day -6 with a -2/+1 day time window (i.e., from Day -8 to Day -5). In Sequence 2 (RT), bosentan and the patient’s diary should be given to the patient on Day -6 of Cycle 2 with a -2/+1 day time window (i.e., from Day 14 of Cycle 1 to Day -5 of Cycle 2).

In addition, the study center will contact the patients (via telephone or other methods) daily during bosentan intake to remind them or confirm that they have taken the morning and evening dose of bosentan when they are not at the study center.

Lurbinectedin

Lurbinectedin will be administered as a 1-hour (-5/+20 min) i.v. infusion on Day 1 q3wk, over a minimum of 100 mL dilution on 5% glucose or 0.9% sodium chloride via a central line (or a minimum of 250 mL dilution if a peripheral line is used).

Patients will receive a maximum of three cycles: two consecutive cycles of lurbinectedin, one cycle with and one cycle without bosentan co-administration (in different order depending on the Sequence 1 or Sequence 2 of treatment), followed by a third cycle with lurbinectedin alone (this last cycle optional for patients with clinical benefit).

The dose of lurbinectedin when given in combination with bosentan will be 3.2 mg/m². Lurbinectedin dose will be based on the acceptability of the PK and safety results from the first three patients.

In cycles with lurbinectedin as single agent, lurbinectedin will be administered at 3.2 mg/m².

7.3 PROPHYLACTIC MEDICATION

All patients will receive standard antiemetic prophylaxis before each treatment infusion (i.e., 30 ± 5 minutes before lurbinectedin administration), i.v. as follows:

- Corticosteroids i.v. (according to institutional standard antiemetic doses, minimum dose of dexamethasone 8 mg/day and maximum dose of 20 mg/day of dexamethasone or equivalent). If feasible, the medication and dose administered in Cycle 1 should be maintained in Cycle 2.
- Serotonin (5-HT₃) antagonists (ondansetron at least 8 mg i.v. and no more than 16 mg of ondansetron).

If necessary, in addition to the above, the duration of treatment with 5-HT₃ antagonists and/or dexamethasone could be extended orally (if needed) (i.e., 4-8 mg/day for three consecutive days) and/or 10 mg of metoclopramide orally every eight hours could be added (according to institutional guidelines).

For the purpose of safety evaluations, optimum prophylaxis is defined as all the aforementioned medications at their respective maximum dose.

Aprepitant or any other NK-1 antagonist or related Substance P-antagonists (except rolapitant) are forbidden while on lurbinectedin treatment.

7.4 CRITERIA FOR TREATMENT CONTINUATION

Patients may continue treatment with lurbinectedin as long as no unacceptable toxicity and/or PD occurred, and for a maximum of three cycles. Thereafter, treatment with lurbinectedin can continue under a Compassionate Use Agreement.

- **Patients assigned to Sequence 1 (TR)** (lurbinectedin + bosentan in Cycle 1), after Cycle 1 the administration of a new cycle should be delayed if the criteria in [Table 7](#) are not met on the corresponding Day 1. Re-assessments will be performed periodically at intervals of at least 72 hours but not more than one week. Lurbinectedin administration should be delayed until recovery of these parameters. A maximum delay of 14 days from the theoretical due date will be allowed for recovery from treatment-related AEs. If recovery has not occurred

after that period, the patient should discontinue the treatment, except in case of obvious patient benefit at the criteria of the Investigator and upon agreement with the Sponsor.

- **Patients assigned to Sequence 2 (RT)** (lurbinectedin + bosentan in Cycle 2), criteria for treatment continuation should be investigated on Day 15 of Cycle 1 in order to confirm bosentan administration start on Day -5 of Cycle 2, assuring that the continuation criteria will be finally met on Day 1 of Cycle 2 assessment. In case of detected abnormalities on Day 15 in sequence RT, these assessments should be repeated every 48-72 hours until recovery to retreatment criteria. Initiation of bosentan will be delayed for a maximum of 14 days to ensure that pre-treatment with bosentan is fulfilled. If recovery has not occurred after that period, the patient should discontinue the treatment, except in case of obvious patient benefit at the criteria of the Investigator and upon agreement with the Sponsor.

Re-treatment criteria for lurbinectedin administration should be met on Day 1 of Cycle 2. If they were not met, treatment will be delayed for a maximum of 2 days to evaluate continuation of lurbinectedin administration, with re-treatment criteria being checked every 24 hours. During this time the patient will continue receiving bosentan. If after 2 days of delay the patient does not meet the criteria for treatment continuation, bosentan will be stopped and the patient will be considered not evaluable for the trial.

If the criteria for treatment continuation are not met as described above, treatment must be discontinued and the EOT visit performed.

Table 7. Criteria for lurbinectedin treatment continuation.

Variable	Lurbinectedin (Day 1)
ECOG PS	≤ 1
ANC	$\geq 1.5 \times 10^9/L$
Platelets	$\geq 100 \times 10^9/L$
Hemoglobin ^a	$\geq 8.0 \text{ g/dL}$
Total bilirubin	$\leq 1.0 \times \text{ULN}$. If it is $> 1.0 \times \text{ULN}$ but $\leq 1.5 \times \text{ULN}$, direct bilirubin must be $\leq 1.0 \times \text{ULN}$
Albumin	$\geq 3.0 \text{ g/dL}$
AST/ALT	$\leq 3.0 \times \text{ULN}$
CPK	$\leq 2.5 \times \text{ULN}$ ($\leq 5.0 \times \text{ULN}$ is acceptable if elevation is disease-related)
Serum Creatinine levels/ Calculated CLcr (Cockcroft and Gault's formula)	Serum creatinine levels $\leq \text{ULN}$ or calculated CLcr $\geq 30 \text{ mL/min}$, if abnormal ($>\text{ULN}$) serum creatinine levels
Other non-hematological drug-related AEs (except isolated increased GGT and/or AP; or grade 2 alopecia, asthenia, peripheral neuropathy and non-optimally treated nausea and/or vomiting)	Grade ≤ 1

^a Patients may receive PRBC transfusions and/or EPO treatment if clinically indicated to increase/maintain adequate hemoglobin levels.

Sequence 1 (TR):

If a patient does not meet the requirements for treatment continuation on Day 1 of further cycles, treatment will be withheld until recovery for a maximum of 14 days after the theoretical treatment date. If recovery has not occurred after a delay of > 14 days, discontinue treatment (except in case of obvious patient benefit at the criteria of the Investigator and upon agreement with the Sponsor).

Variable	Lurbinectedin (Day 1)
----------	-----------------------

Sequence 2 (RT):

If a patient does not meet the requirements for treatment continuation on Day 15 of Cycle 1, treatment with bosentan will be withheld until recovery for a maximum of 14 days after the theoretical treatment date. If recovery has not occurred after a delay of > 14 days, discontinue treatment (except in case of obvious patient benefit at the criteria of the Investigator and upon agreement with the Sponsor).

If a patient does not meet the requirements for treatment continuation on Day 1 of Cycle 2, treatment with lurbinectedin will be withheld until recovery for a maximum of 2 days after the theoretical treatment date. During this time, the patient will continue receiving bosentan. If recovery has not occurred after a delay of > 2 days, bosentan will be stopped and the patient will be considered not evaluable for the trial.

AEs, adverse events; ALT, alanine aminotransferase; ANC, absolute neutrophil count; AP, alkaline phosphatase; AST, aspartate aminotransferase; CLcr, creatinine clearance; CPK, creatine phosphokinase; ECOG PS, Eastern Cooperative Oncology Group Performance Status; EPO, erythropoietin; GGT, gamma glutamyltransferase; PRBC, packed red blood cells; UULN, upper limit of normal.

7.5 DOSE REDUCTION

Patients may continue in the study treatment at a lurbinectedin reduced dose if they present any of the following:

- Grade 4 thrombocytopenia or grade 3 thrombocytopenia concomitantly with grade \geq 3 bleeding.
- Two dose delays or prolonged (> one week) dose delay due to treatment-related adverse events.
- Grade \geq 3 treatment related non-hematological toxicity. Exceptions are: grade \geq 3 nausea and/or vomiting not optimally treated, grade 3 fatigue lasting < two days, grade 3 diarrhea lasting < one day or non-optimally treated, isolated grade 3 transient ALT/AST elevations which are rapidly reversible and not leading to subsequent delays and, non-clinically relevant isolated biochemical abnormalities.
- Grade 4 neutropenia or any grade febrile neutropenia.

Up to two dose reductions are allowed per patient. Patients who continue to experience treatment-related toxicity and/or dose delays after two dose reductions must be withdrawn from the study. Once the dose has been reduced for an individual patient, it will not be re-escalated under any circumstances.

Lurbinectedin dose reduction levels are shown in [Table 8](#).

Table 8. Levels of (intra-patient) lurbinectedin dose reduction in subsequent cycles.

Dose reduction	Lurbinectedin (q3wk) (mg/m ²)	
	Lurbinectedin alone	Bosentan co-administration cycle
1 (starting dose)	3.2	3.2
-1	2.6	2.6
-2	2.0	-

Lurbinectedin total doses in mg will be rounded to the first decimal, if necessary.
q3wk, every three weeks.

Patients who experience any treatment-related grade 3/4 hypersensitivity and/or extravasation reactions will permanently discontinue treatment.

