*** Permitted windows for assessments before Day 1 of Cycle 1:**

If physical examination, ECOG PS, vital signs, Hematology, Biochemistry-A, Biochemistry-B, CLcr (provided only if serum creatinine levels are above ULN) and Coagulation were assessed >10 days before Day 1 of Cycle 1, the tests must be repeated the day before or the Day 1 (always prior to lurbinectedin infusion).

If pregnancy test was done >7 days before Day 1 of Cycle 1, the test must be repeated the day before or the Day 1 (always prior to lurbinectedin infusion).

A patient should only be treated if eligibility criteria are still met according to assessments performed closest to treatment start.

Permitted windows for assessments after Day 1 of Cycle 1:

A ± 2-day time window will be allowed for Hematology, Biochemistry-A and CLcr (provided only if serum creatinine levels are above ULN) on Day 8 and Day 15, and for vital signs on Day 8 of Cycle 1.

A -1 day window will be allowed for physical examination, ECOG PS, vital signs, Hematology, Biochemistry-A, and Biochemistry-B, CLcr (provided only if serum creatinine levels are above ULN) and Pregnancy test on Day 1 of Cycle 2 and further cycles (always prior to lurbinectedin infusion).

A + 2 days window for Day 1 lurbinectedin administration of Cycle 3.

If a drug administration is delayed beyond the permitted protocol window, assessments planned for the original administration day must be repeated on the day the dose is finally administered.

^a Should treatment be administered more than ten days after the screening tests, repeat these tests prior to the first infusion and if clinically indicated. Height needs to be measured at baseline only. BSA will not be reported at the EOT. BSA calculated according to DuBois formula (see [Appendix 4](#)).

^b In case of detected abnormalities on Day 15 in sequence RT, these assessments should be repeated every 48-72 hours until recovery to retreatment criteria. Initiation of cycle 2 will be delayed accordingly in order to ensure that pre-treatment with bosentan is fulfilled.

^c Repeat during treatment period and at EOT if clinically indicated.

^d Calculated CLcr [Cockcroft and Gault's formula] should be provided only if serum creatinine levels are above ULN.

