7.4 Treatment Administration

Exposure to treatment will be described by treatment group.

Total cumulative dose, time on treatment, dose intensity and relative dose intensity, administration delay and dose reductions/omissions will be described following standard tables (detailed in Section 11, Appendix II). The reported cycle information on the case report form (CRF) pages will be used for the analysis.

Time on treatment, expressed in weeks, is defined as the last administration date of lurbinecetin minus the first administration date plus 31 days, except if the patient dies or starts a new antitumor therapy within 31 days from the last administration date, in which case the time on treatment will be the date of death or the start date of the new antitumor therapy minus the date of the first administration of the study treatment.

Total cumulative dose by drug, expressed in mg for both lurbinecetin and bosentan, is the sum of all the product doses received during the study, including the dose received in the last cycle.

For lurbinecetin, intended dose intensity is the planned dose per cycle divided by the planned number of weeks by cycle.

Absolute dose intensity is the actual cumulative dose divided by the number of weeks of treatment. As a convention, for this calculation, the duration of the last cycle will be the predefined cycle length (e.g. 21 days). Relative dose intensity (%) is the ratio of absolute dose intensity divided by the intended dose intensity.

The items « Infusion delayed: yes/no» and « Dose reduced: yes/no» present on the treatment exposure CRF pages will be used to calculate delays and dose reductions, respectively. For cycles considered as delayed by the Investigator, the length of the delay will be calculated as:

Duration of cycle delay: Date of the current drug administration – Date of the previous drug administration – the predefined cycle length (i.e., 21 days).

If the number of delays or dose reductions are very low, tables will not be presented and only listings will be shown.

7.5 *Subsequent Therapies*

A listing of subsequent therapies received after treatment discontinuation will be shown by total and treatment sequence group.

7.6 *Subgroup Analyses*

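### The SAP delay formula includes the bosentan lead-in given after recovery, so the same recovery day can give up to about 5 more delay days in Sequence 2 than in Sequence 1

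*Protocol*

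**What the plan says.** **Sequence 1 (bosentan in Cycle 1).** Under Protocol 7.4, Cycle 2 lurbinectedin is held until the Table 7 criteria are met. Re-tests are 72 hours to one week apart, and the limit is 14 days from the lurbinectedin due date.

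**Sequence 2 (bosentan in Cycle 2).** The criteria are first examined on Day 15 of Cycle 1, before bosentan starts: "In case of detected abnormalities on Day 15 in sequence RT, these assessments should be repeated every 48-72 hours until recovery to retreatment criteria". Footnote b of the Sequence 2 schedule of assessments adds: "Initiation of cycle 2 will be delayed accordingly in order to ensure that pre-treatment with bosentan is fulfilled". Section 7.2 gives bosentan "twice daily in the morning and in the evening from Day -5 to Day -1". Section 7.4 sets the limit as "Initiation of bosentan will be delayed for a maximum of 14 days to ensure that pre-treatment with bosentan is fulfilled", and the Table 7 note as "treatment with bosentan will be withheld until recovery for a maximum of 14 days after the theoretical treatment date". If the criteria fail on Day 1 of Cycle 2, a further hold of at most 2 days is allowed.

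**Consequences of a delay.** Section 7.5 applies one trigger to both sequences: "Two dose delays or prolonged (> one week) dose delay due to treatment-related adverse events". Section 5.2.1.2 lists a delay of more than 14 days due to treatment-related events as a reason to stop, with a clinical-benefit exception.

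**Counting.** SAP 7.4 says: "For cycles considered as delayed by the Investigator, the length of the delay will be calculated as" "Date of the current drug administration – Date of the previous drug administration – the predefined cycle length (i.e., 21 days". Delays are tabulated by sequence and reason in Table 11.1.2.1, and by sequence and length (up to 7, over 7 to 14, over 14 days) in Table 11.1.2.2. AE-associated delays are shown by treatment in Table 11.2.1.1.

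**The concern.** The two sequences have to meet the same criteria at different times. Sequence 1 needs them on the day of infusion; Sequence 2 needs them before a five-day lead-in. The SAP formula looks only at infusion dates. Once a Sequence 2 Cycle 2 is marked as delayed, its length therefore includes bosentan days given after the patient has recovered.

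Delays due to adverse events are part of a stated secondary safety endpoint (Protocol 3.4.2, SAP 4.2.2). With about four patients per sequence, one or two reclassified patients change the table. The extra days belong to the bosentan cycle. If a delay is assigned to the cycle whose exposure page records it, they fall in the BOS+LRB column of Table 11.2.1.1, although the toxicity arose after lurbinectedin alone.

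**Working it through.** The plan gives no figure of its own to reproduce here; the check is calendar arithmetic.

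**Inputs.** Cycle length is 21 days (SAP 7.4). Lead-in runs from Day -5 to Day -1 (Protocol 7.2). Cycle 1 Day 1 is day 1, so planned Cycle 2 Day 1 is day 1 + 21 = 22. With no Day 0, Day -5 is 22 − 5 = day 17. The bosentan dispensing window agrees: two days before Day -6 is Day -8, which is 22 − 8 = day 14, as stated. (The schematic's equation of Day 15 with Day -6 is one day off this count, within the ±2-day visit window.)

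**Formulas.** Let r be the day the Table 7 criteria are first met, with treatment following at once.

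- Sequence 1: infusion on max(22, r); delay = max(0, r − 22).
- Sequence 2: bosentan starts on max(17, r) and infusion is 5 days later; delay = max(17, r) + 5 − 22 = max(0, r − 17).

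| r | Sequence 1 delay (days) | Sequence 2 delay (days) | Difference |
|---|---|---|---|
| 17 or earlier | 0 | 0 | 0 |
| 18 | 0 | 1 | 1 |
| 20 | 0 | 3 | 3 |
| 22 | 0 | 5 | 5 |
| 25 | 3 | 8 | 5 |
| 29 | 7 | 12 | 5 |
| 31 | 9 | 14 | 5 |

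If bosentan starts the day after recovery is confirmed, the gap reaches 6 days. For r = 25 to 29 the Table 11.1.2.2 category differs: 3–7 days against 8–12.

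**Re-testing.** After day 22 the date of detection matters. Suppose Sequence 1 is tested weekly (days 22, 29, 36). True recovery on day 25 is then found on day 29, a delay of 7 days; Sequence 2, if it is detected on day 25, has 8. True recovery on day 30 is found on day 36 in Sequence 1 (14 days); Sequence 2, if detected on day 30, is infused on day 35 (13 days). The gap has reversed.

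**Relative dose intensity.** SAP 7.4 divides by actual weeks and sets the last cycle to 21 days. Two full-dose cycles with r = 22 take 21 + 21 = 42 days in Sequence 1 (100%) and 26 + 21 = 47 days in Sequence 2 (42/47 = 89%).

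**Reduction trigger (over 7 days).** With lead-in days counted, it is met from r = 30 in Sequence 1 and from r = 25 in Sequence 2. If only time from day 22 to recovery is counted, it is r = 30 in both.

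**Stop.** Sequence 1 allows recovery to day 22 + 14 = 36. Sequence 2 allows day 17 + 14 = 31 if the theoretical treatment date is the bosentan date, or day 36 if it is the lurbinectedin date. Section 5.2.1.2, applied to infusion dates with the lead-in included, gives r + 5 − 22 > 14, so r = 32 or later. A 14-day bosentan delay plus the 2-day allowance is 16 days, against the 14-day limit in 5.2.1.2.

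**Illustration only.** Assume r is normal with SD 3 and mean 15, 17 or 19; the documents give no such distribution. The share with any delay is P(r > 22) = 1.0%, 4.8%, 15.9% in Sequence 1 and P(r > 17) = 25%, 50%, 75% in Sequence 2. The share passing 7 days in Sequence 2 is P(r > 24) = 0.1%, 1.0%, 4.8%.

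**The case against.** The SAP formula gives a length, and only for cycles the investigator marks as delayed. The reason is recorded separately: Table 11.1.2.1 has an other-reason row and Listing 11.1.2.3 shows the reason for each delay. This stands as far as it goes, but no rule divides one delay between recovery and lead-in, so investigators may label it differently.

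The protocol reports that neutropenia rarely caused delays in the first-in-human study, and SAP 7.4 replaces the delay tables with listings if delays are very few. Both limit the practical effect. That study, as described, did not require recovery before a lead-in.

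Toxicity present at the planned bosentan start is what postpones Cycle 2, so relabelling those days as scheduling would hide a toxicity-caused postponement. This is right, and it is why the total must be kept.

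Three stronger readings are tempting and are not supported:

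- *That the protocol counts the lead-in as toxicity delay and so reduces the dose of bosentan cycles for a non-toxicity reason.* Section 7.5 is silent on lead-in days and permits a reduction without compelling it. At r = 25 to 29 toxicity has also lasted 3 to 7 days past the due date, and two delays cannot have occurred before Cycle 2.
- *That counting the lead-in causes an earlier stop in Sequence 2.* The earlier stop in 7.4 and Table 7 depends on which date anchors the 14-day limit, and the stop rules have a patient-benefit exception.
- *That Sequence 2 delays are longer by construction for every recovery day.* Beyond day 22 the different re-test intervals can offset the gap.

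**Conclusion.** The point holds for the SAP's delay lengths. For recovery on days 18 to 22, Sequence 1 has no delay and Sequence 2 has 1 to 5 days; after day 22 the difference is up to about 5 days and may shrink or reverse. This assumes no Day 0, bosentan starting on the day of recovery, and the investigator marking the cycle as delayed.

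The effect is confined to descriptive output: Tables 11.1.2.1 and 11.1.2.2, the AE-delay rows of Table 11.2.1.1, and relative dose intensity. The safety model in SAP 11.5 does not use delays. The primary PK endpoint is dose-normalized and evaluability does not depend on delays or reductions, although a patient stopped before Cycle 2 would be non-evaluable and replaced. An earlier reduction trigger in Sequence 2 is possible because 7.5 leaves the count undefined; the protocol does not state one.

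**What to change.** **SAP 7.4 and the tables named above.** Keep the total delay. Add a split defined identically in both sequences: (a) days from day 22 to the first date the continuation criteria are documented as met, and (b) the remaining days for bosentan lead-in. For r = 25 this gives 3 + 0 in Sequence 1 and 3 + 5 in Sequence 2; for r = 20, 0 + 0 and 0 + 3. State which items (laboratory values, ECOG PS, AE grade) define documented recovery, since laboratory dates alone do not cover Table 7. State where the 2-day hold on Day 1 is counted, and footnote the different re-test intervals.

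**Protocol.** Sections 7.4, Table 7, 7.5 and 5.2.1.2 must be reconciled on how delay is counted in each sequence and from which date the 14-day limit runs, including the 16-day case. Which rule applies is for the sponsor's clinicians.

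**Cost.** One extra derived variable, a slightly more complex table and a short protocol clarification.
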